A prospective cohort study is to be conducted at the MRRH Division of Neurosurgery and Mayanja Memorial Hospital (MMH) from May 2024 until May 2025 or until our sample size has been met. Prior to the study, approval from the following institutions and administrations will occur; Duke University IRB approval, Mbarara University of Science and Technology (MUST) IRB approval, Uganda National Council for Science and Technology (UNCST) approval, and administrative approval from both hospitals will be collected.

Methods & Procedures

When applicable (conscious patient and/or family or legally authorized representative (LAR), the study will be introduced to the patient and relevant parties before the research team approaches the patient. While head trauma frequently results in impaired cognition and/or consciousness, and due to the urgency of these circumstances, patients are often not accompanied by kin, whenever appropriate, the purpose of the research and the procedure will be explained in detail using an IRB-approved verbal consent “script”, with all questions answered to the patient’s and/or representative’s satisfaction.

Upon presentation to the casualty unit at MRRH or MMH and/or within 30 minutes prior to or following a CT scan, the study team will approach the patient or the patient’s LAR for permission to scan the patient’s cranium with the InfraScanner 2500™ (Image A). If permission is granted, the study team member will sequentially measure the optical absorption for each of the 8 quadrants of the scalp (frontal, temporal, parietal, and occipital bilaterally) (Image B). The device is engineered such that the light emitter and receiver are spaced 4 cm apart, allowing the light’s intensity to be measured between adjacent light guides (Image C). Parting combs will be used to help access the scalp on patients with hair that prevents the fiberoptic tips from direct contact with the scalp. A laminated swatch displaying Monk Skin Tone Orbs will be used for later analysis of skin tone on the Monk Skin Tone Scale (Image

D).²⁶ This entire procedure, including greeting, scanning the patient, should take <10 minutes. Basic demographics, neuro exam, and InfraScanner 2500™ data will be entered into REDCap (Appendix A).

The collection period for each research subject concludes within 30 days following his or her initial consent, patient or LAR decision to withdraw from further participation, hospital discharge, or patient death, whichever occurs first.

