6. **Eligibility:** Any patient aged 12 and up who presents to Mbarara Regional Referral Hospital (MRRH) or Mayanja Memorial Hospital (MMH) with suspected head trauma, who is able to or who has a LAR who is able to consent in English, Runyankole, or Luganda will be considered for this study. After being made aware of the study by a physician directly caring for the patient and agreeing to hear more about the study, the prospective participant and/or the participant's LAR will be approached.
7. **Exclusion:** Patients for which wounds to their head are too large to properly use the InfraScanner 2500™ will be excluded from this study. Patients will also be excluded if hair cannot be appropriately parted to allow for the fiberoptic tips of the device to make direct contact with the scalp. Patients for whom it is not possible to obtain an Infrascan within 30 minutes of their CT imaging will also be excluded from the study.
8. **Subject Recruitment and Compensation:** Potential research participants will be approached by the research team only if given permission by the physician in charge of the patient's care after he or she has informed the patient and/or the patient's LAR of the research and received a verbal agreement from the patient and/or LAR to hear more about the research study. Each participant will be compensated UGX 15,000 (\$4) for participation in this study. The study personnel will be trained in the consent process and will make it abundantly clear that agreement or refusal to participate in the study will not influence the patient's care in any way.

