- 15. Statistical Considerations:** Objectives: The primary objective of this study is to estimate the test characteristics (sensitivity, specificity, and the false positive and false negative rates) of the portable NIR-based device (InfraScanner 2500™) in the identification of any size hematoma among patients hospitalized at MRRH or MMH who have sustained or who are suspected of having sustained head trauma. CT scan results will serve as the gold standard. The sensitivity, specificity, and false positive and false negative rates will be estimated. Continuous variables will be summarized with means/medians, standard deviations, and ranges, and will be analyzed using one-way analysis of variance (ANOVA). Categorical variables will be summarized with frequency counts and percentages and analyzed using the χ^2 test or Fisher's exact test where appropriate. Sensitivity, specificity, false-positive, and false-negative values will be calculated for InfraScanner 2500™ versus CT as a gold standard, with an estimated 95% confidence interval (CI). Receiver operating characteristic (ROC) curves and area under the curve (AUC) with 95% CI will be plotted. Logistic regression will be fit to examine the association between InfraScanner 2500™ results (conditioned on CT results) and potential confounders such as age, sex, skin color, hair length, hairstyle, skull fracture, scalp laceration, polytrauma, and scalp hematoma. Minimum blood volume detected as positive by InfraScanner 2500 (minimum resolution) will be reported. All statistical tests will be two-sided, and significance will be assessed at $\alpha = 0.05$. Analyses will be performed using R (Boston, MA).

A secondary objective is to estimate the test characteristics of the InfraScanner 2500™ in the identification of hematomas within its detection limits (volume >3.5 mL and depth <2.5 cm) compared to CT scan results as the gold standard.

Exploratory objectives include:

1. Examining the impact of factors such as hematoma type, location, patient age, and skin tone on test characteristics of the InfraScanner 2500™
2. Determining the minimum resolution detectable by the InfraScanner 2500™
3. Analyzing the effects of extracranial hematomas, lacerations, and swelling on the device's performance characteristics
4. Estimating Receiver Operating Characteristic (ROC) curves

Study Design:

a) Eligibility:

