Appendix A

Variable	Type	Description	FITBR Harmonization-Variable Name
finished	T/F	Details if the survey was completed	
ra	Text Entry	Name of Research Assistant completing the survey	
name	Text Entry	Name of patient	
id	Text Entry	Study ID number of patient	SubjectIDNum
age	Numeric	Age of patient	AgeYrs
sex	M/F	Sex of patient	GenderTyp
skin tone	Numeric	Monk Skin Tone Scale (1-10)	
region	Dropdown	Region of Uganda where patient lives	CntryResdnceName
district	Dropdown	District of Uganda where patient lives	
country_other	Text Entry	Country of residence if not Uganda	CntryResdnceName
study_site	Dropdown	Name of site where patient enrolled	SiteName
admit_month	Dropdown	Month of admission	VisitDate
admit_day	Dropdown	Day of the month of admission	VisitDate
admit_year	Dropdown	Year of admission	VisitDate
admit_hours	Numeric	Hour of admission (using 24 hour timing)	ScreenVisitDateTime
admit_mins	Numeric	Minute of the hour of admission (up to 59 mins)	ScreenVisitDateTime
temp	Numeric	Temperature on admission	
admit_eye	Numeric	Admit GCS eye opening	GCSEyeRespnsScale
admit_verbal	Numeric	Admit GCS verbal	GCSVerbalRspnsScale
admit_motor	Numeric	Admit GCS motor	GCSMotorRespnsScale
admit_gcs	Numeric	Admit GCS total	GCSTotalScore
neuro_month	Dropdown	Month of neuro exam	
neuro_day	Dropdown	Day of the month of neuro exam	
neuro_year	Dropdown	Year of neuro exam	
neuro_hours	Numeric	Hour of neuro exam (using 24 hour timing)	
neuro_mins	Numeric	Minute of the hour of neuro exam (up to 59 mins)	

infra_eye	Numeric	Infrascanner GCS eye opening	GCSEyeRespnsScale
infra_verbal	Numeric	Infrascanner GCS verbal	GCSVerbalRspnsScale
infra_motor	Numeric	Infrascanner GCS motor	GCSMotorRespnsScale
infra_gcs	Numeric	Infrascanner GCS total	GCSTotalScore
injury_month	Dropdown	Month of TBI	InjDateTime
injury_day	Dropdown	Day of the month of TBI	InjDateTime
injury_year	Dropdown	Year of TBI	InjDateTime
injury_hours	Numeric	Hour of neuro exam (using 24 hour timing)	
injury_mins	Numeric	Minute of the hour of neuro exam (up to 59 mins)	
hair_scalp_access	Y/N	hair status occludes access to scalp	
hair_scalp_access_reason	Text Entry	Text entry if hair status did not allow for access to scalp	
trauma	Dropdown	Cause of trauma	
trauma_other	Text Entry	Text entry if cause of trauma was not listed	
polytrauma	Y/N	Polytrauma present	
rta	Dropdown	Cause of road traffic accident	
rta_other	Text Entry	Text entry if cause of RTA was not listed	
scalp	Y/N	Scalp or face hematoma present	

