scalp_text	Text Entry	Location of scalp or facial hematoma	
facial_bleed	Multi-select	Bleeding from eyes, ears, or nose present	
skull	Y/N	Skull fracture present	
skull_bones	Multi-select	Location of skull fracture	
scalp_injury	Y/N	Open scalp injury present	
surgery_planned	Y/N	A surgery was planned	
surgery	Y/N	A surgery was completed	
surgery_month	Dropdown	Month of surgery	
surgery_day	Dropdown	Day of the month of surgery	
surgery_year	Dropdown	Year of surgery	
surgery_type	Multi-select	Type of surgery performed	
surgery_type_other	Text Entry	Text entry if surgery type not listed	

ct	Y/N	A CT was completed	
ct_month	Dropdown	Month of CT	
ct_day	Dropdown	Day of the month of CT	
ct_year	Dropdown	Year of CT	
ct_hours	Numeric	Hour of CT (using 24 hour timing)	
ct_mins	Numeric	Minute of the hour of CT (up to 59 mins)	
ct_no	Multi-select	Details why a CT was not completed	
ct_no_other	Text Entry	Text entry for no CT if not listed	
infra_1_month	Dropdown	Month of first infrascanner	
infra_1_day	Dropdown	Day of the month of first infrascanner	
infra_1_year	Dropdown	Year of first infrascanner	
infra_1_hours	Numeric	Hour of first infrascanner (using 24 hour timing)	
infra_1_mins	Numeric	Minute of the hour of first infrascanner (up to 59 mins)	
infra_1_positive	Y/N	First infrascanner with a positive result	
infra_1_frontal	Numeric	First infrascanner numeric result in frontal area	
infra_1_parietal	Numeric	First infrascanner numeric result in parietal area	
infra_1_temporal	Numeric	First infrascanner numeric result in temporal area	
infra_1_occipital	Numeric	First infrascanner numeric result in occipital area	
outcome_month	Dropdown	Month of outcome	
outcome_day	Dropdown	Day of the month of outcome	
outcome_year	Dropdown	Year of outcome	
outcome	Dropdown	Outcome of patient	
disc_eye	Numeric	Discharge GCS eye opening	GCSEyeRespnsScale
disc_verbal	Numeric	Discharge GCS verbal	GCSVerbalRespnsScale
disc_motor	Numeric	Discharge GCS motor	GCSMotorRespnsScale
disc_gcs	Numeric	Discharge GCS total	GCSTotalScore

gose	Numeric	GOSE on discharge	GlasgowOutcomeScaleExtScore
ct_pos	Y/N	CT with positive findings	
ct_fl	Dropdown	Type of bleed on CT frontal left	
ct_fr	Dropdown	Type of bleed on CT frontal right	
ct_pl	Dropdown	Type of bleed on CT parietal left	
ct_pr	Dropdown	Type of bleed on CT parietal right	
ct_tl	Dropdown	Type of bleed on CT temporal left	
ct_tr	Dropdown	Type of bleed on CT temporal right	
ct_ol	Dropdown	Type of bleed on CT occipital left	

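### Hair length and hairstyle are named as regression covariates, but the Appendix A data list has no field for either

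*Combined protocol and SAP*

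**What the plan says.** The Objectives paragraph of section 15 plans a logistic regression for the association between the InfraScanner result, given the CT result, and "potential confounders such as age, sex, skin color, hair length, hairstyle, skull fracture, scalp laceration, polytrauma, and scalp hematoma". That is nine named covariates, two of them about hair.

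The Methods & Procedures part of section 5 names the data source: "Basic demographics, neuro exam, and InfraScanner 2500™ data will be entered into REDCap (Appendix A". Appendix A is therefore the plan's list of what is captured.

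Appendix A has two hair items. `hair_scalp_access` (Y/N) is described as "hair status occludes access to scalp". `hair_scalp_access_reason` is described as "Text entry if hair status did not allow for access to scalp".

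Elsewhere hair appears only as a practical matter: parting combs in section 5, an exclusion in section 7 ("Patients will also be excluded if hair cannot be appropriately parted"), and the reach of the optical fibres in section 12. None of these sections says that length or style will be recorded.

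**The concern.** The plan commits to examining two patient characteristics that its own data list does not capture. A team that follows the protocol and Appendix A exactly will reach the analysis without them.

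Hair is a plausible covariate on the plan's own account, since section 5 recognises that it can keep the fibre tips off the scalp. Skin tone is also central to the rationale. The Background reports 38% specificity at MRRH against 96% at DUH with the earlier device, and suggests skin tone as one explanation for the false positives. Skin tone is then an exploratory factor in section 15. If hair were related both to skin tone and to false-positive readings, its effect could not be separated from that of skin tone without hair data. Hair is best observed at the scan, and enrolment was planned from May 2024.

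**Working it through.** The plan states no figure on this point, so the main check is a match of each named covariate against all 94 rows of Appendix A.

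| Covariate in section 15 | Field in Appendix A |
|---|---|
| Age | `age` |
| Sex | `sex` |
| Skin color | `skin tone` (Monk scale, 1-10) |
| Skull fracture | `skull` (Y/N) |
| Polytrauma | `polytrauma` (Y/N) |
| Scalp laceration | near match: `scalp_injury`, "Open scalp injury present" |
| Scalp hematoma | near match: `scalp`, "Scalp or face hematoma present"; site in free text, "Location of scalp or facial hematoma" |
| Hair length | none |
| Hairstyle | none |

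Seven of nine have a field or near match and two have none. Of the 94 variables, 2 concern hair and 0 record length or style. The access item measures obstruction, and its free-text companion is filled only when access failed.

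**Possible bias (illustration only).** The documents give no hair data, so every hair input here is assumed: one binary hair factor with prevalence 40%, an odds ratio of 2 to 3 for a false positive, and no true skin-tone effect. The false-positive share is 62% (from the 38% MRRH specificity) or an assumed 20%. CT-negatives: 171 × 0.54 ≈ 92. No other covariate is in the model.

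| Hair–skin-tone correlation | Skin-tone odds ratio per SD, hair omitted | Null trials significant at 0.05, hair omitted |
|---|---|---|
| 0 | 1.00 | 4–5% |
| ±0.2 | 1.06–1.11, or 0.90–0.94 | 5–6% |
| ±0.4 | 1.14–1.25, or 0.81–0.88 | 8–15% |

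With hair in the model the rejection rate is 4–5% throughout. If 0.4 is instead read as the correlation with a latent continuous hair variable, 8–15% becomes about 7–11%. The simulation was repeated and agrees within simulation error.

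**Precision cost in CT-negatives (same kind of illustration).** One binary hair factor widens the skin-tone standard error by about 2–13%, for example from 0.222 to 0.227 at zero correlation and from 0.225 to 0.252 at 0.4. Two three-level fields unrelated to skin tone widen it by roughly 5–7%.

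**Sparseness in CT-positives.** Inputs are 84 CT-positives (section 15) and 89% sensitivity (earlier device at MRRH, Background).

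- Expected false negatives: 84 × (1 − 0.89) = 84 × 0.11 ≈ 9. Using 46% of 171 instead gives 79 × 0.11 ≈ 9, the same answer.
- Seven covariates with one coefficient each: 9/7 ≈ 1.3 events per coefficient.
- Two three-level hair fields add 4 coefficients: 9/11 ≈ 0.8.
- Two two-level hair fields add 2 coefficients: 9/9 = 1.0.

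The CT-positive model is too sparse for ordinary maximum likelihood even before hair is added.

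**The case against.** The strongest reply is that this is a small mismatch at the edge of the plan. The covariate list is introduced as illustrative. Section 5 does not say that nothing outside Appendix A is recorded, and section 17 mentions experimenters' notes. Hair is in none of the four exploratory objectives, combs and fibre design reduce its influence, and accuracy in darker-skinned patients (Aim 2) can be estimated without a hair-adjusted coefficient.

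Much of this limits the reach of the point, but it does not remove it. An illustrative list may be extended, yet the two hair covariates are named and the data list cannot supply them. Nothing says that the notes record hair. Combs and fibres mitigate an effect without measuring it.

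Four stronger readings are tempting and are not supported:

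- *The access item is constant among analysed patients because of the section 7 exclusion.* Appendix A does not say whether it is scored before or after parting. If before, enrolled patients could be scored Y. It would still not be length or style.
- *The skin-tone result will be biased.* That needs hair to be related to both skin tone and false positives, and the documents give no data on either. In the illustration, rejection is near nominal at correlations of 0 to 0.2. Covariates already planned, such as age and sex, might absorb part of any hair effect.
- *Hair data are lost once the scan is over.* Follow-up runs to discharge, death, withdrawal or 30 days, so hair could still be noted for patients in hospital unless it has been cut.
- *The accuracy results are undermined.* The sensitivity and specificity estimates do not use hair.

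**Conclusion.** The point holds as an inconsistency between the analysis and the data list: 2 of 9 named covariates have no field, and neither existing hair item can stand in for them. This rests on a direct reading of section 15 and Appendix A and on taking Appendix A as the REDCap content, as section 5 does.

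Its reach is limited to the covariate regression and the exploratory skin-tone analysis. The consequence for the skin-tone estimate cannot be sized from the documents. It is nil if hair is unrelated to skin tone or to false positives, and the illustrative figures depend wholly on assumed inputs. The change is still worth making, because following the plan exactly forgoes covariates that it names, and the remedy is cheap while patients are being scanned. The sparseness conclusion assumes that the earlier device's sensitivity carries over to the new one.

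**What to change.** **Preferred.** Add hair length and hairstyle to Appendix A and the case report form as coded fields with two or three levels each, recorded at the InfraScan, and use them in the section 15 regression. For patients already scanned, report the fields as missing where hair was not noted.

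**If the fields cannot be added.** Remove the two covariates from section 15 and state that skin-tone results are not adjusted for hair. Either repair makes the two sections consistent. Only the first allows hair to be examined.

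**Cost.** A few seconds per scan, within a procedure planned to take under 10 minutes, and the modest loss of precision for skin tone in CT-negatives shown above. In CT-positives, with about 9 false negatives expected, name in advance a penalised (Firth) fit or a reduced covariate set. The same provision would be needed in CT-negatives if specificity proves high: at the 96% seen at DUH, 92 × 0.04 ≈ 4 false positives would be expected.

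### Exploratory objective 3: swelling has no data field, and extracranial hematoma is coded only as a merged scalp-or-face flag with no rule linking its location text to the scanned sites

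*Combined protocol and SAP*

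**What the plan says.** Section 15 (Statistical Considerations) lists as its third exploratory objective "Analyzing the effects of extracranial hematomas, lacerations, and swelling on the device's performance characteristics". The logistic regression described earlier in that section takes the device result, conditional on CT, as outcome. Its list of possible confounders includes "skull fracture, scalp laceration, polytrauma, and scalp hematoma". Swelling is not in that list, although the list is introduced as examples only.

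Section 5 sends the study data to REDCap and refers to Appendix A for the fields. The relevant ones are:

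- `scalp`, yes/no, one per patient: "Scalp or face hematoma present".
- `scalp_text`, free text: "Location of scalp or facial hematoma".
- `scalp_injury`, yes/no, one per patient: "Open scalp injury present".
- `infra_1_positive`, one overall yes/no device result, plus one number for each of four areas, for example "First infrascanner numeric result in frontal area".

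Section 12 explains that the device compares left with right in four areas. The probe positions are the forehead, the temporal fossa, above the ear and behind the ear.

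**The concern.** The device reads greater absorption on one side as a hematoma. Blood outside the skull but under one probe could plausibly produce the same left-right difference. Whether it does is what objective 3 asks, and the answer bears on how false positives are interpreted: with the earlier model at MRRH, Section 4 reports a specificity of 38%, against 96% at DUH.

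The exposure that matters is therefore blood or swelling at a probe site. The form does not capture that directly. One of the three named factors is not recorded. For another, the only coded variable puts a cheek or jaw hematoma, which is under no probe, in the same category as a temporal one, which is. If that flag were the covariate, the estimated effect would be too small and an exploratory null result would be hard to read.

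**Working it through.** **Step 1: match each factor in objective 3 to the data.** The plan gives no figure on this point to reproduce, so the check sets the objective beside the fields.

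| Factor | Coded field | Location | Named as covariate |
|---|---|---|---|
| Extracranial hematoma | `scalp` (scalp and face merged) | `scalp_text`, uncoded | Yes, as scalp hematoma |
| Laceration | `scalp_injury` | None | Yes, as scalp laceration |
| Swelling | None | None | No |

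Swelling has no source. Laceration has one at patient level. Hematoma has a flag and a text entry, but the flag is wider than the covariate named in Section 15, and no rule says how the text narrows it.

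**Step 2: what happens if the flag is used alone.** Among CT-negative patients, let a be the false-positive proportion with no blood under a probe, b the proportion with blood under a probe, and f the share of flagged patients whose hematoma is only on an unscanned part of the face. Assume that those patients have proportion a. Then

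observed difference = (1 − f)b + fa − a = (1 − f)(b − a).

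The relative loss is f, whatever a and b are.

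**Step 3: illustrations.** None of a, b or f is in the documents; all are assumed. The first case takes a = 15% and b = 40% (25 points), the second a = 15% and b = 50% (35 points).

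| f | True difference 25 points | True difference 35 points |
|---|---|---|
| 0 | 25.0 | 35.0 |
| 10% | 22.5 | 31.5 |
| 25% | 18.75 | 26.25 |
| 50% | 12.5 | 17.5 |
| 75% | 6.25 | 8.75 |

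**Step 4: effect on power in the 35-point case.** Inputs from Section 15 are 171 evaluable patients (taken as stated), 46% with hematoma, and two-sided α = 0.05. CT-negative patients: 171 × 0.54 = 92.3, taken as 92. The share of these who are flagged is assumed at 20% (n₁ = 18.4) or 40% (n₁ = 36.8), with n₂ the remainder. With d the observed difference, p₁ = a + d and p₂ = a,

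power = Φ[(d − 1.96·SE₀)/SE₁],

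where SE₀ uses the pooled proportion and SE₁ the separate ones.

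| f | Power, 20% flagged | Power, 40% flagged |
|---|---|---|
| 0 | 0.87 | 0.95 |
| 10% | 0.80 | 0.91 |
| 25% | 0.68 | 0.80 |
| 50% | 0.42 | 0.51 |

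**Step 5: what happens if the text is coded.** If `scalp_text` is complete enough to separate face-only cases, f returns to 0 and this source of dilution disappears. The loss in Steps 3 and 4 therefore depends on how the fields are used and how well the text is filled in.

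**The case against.** The case for the plan is substantial. Two of the three factors do have fields. A location entry sits directly after the hematoma flag, and Section 15 names scalp hematoma, not scalp-or-face hematoma, as the covariate. Nothing says that the raw flag will be used. Section 15 ties no analysis to any Appendix A variable name, so its silence on `scalp_text` proves little. The objective itself speaks of extracranial hematomas, which includes facial ones. Because one probe pair sits on the forehead, which a research assistant might well call face, a merged screening question followed by location avoids losing those cases. The objective is exploratory, and no sample size or decision rests on it.

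Most of this stands. It rules out two stronger readings that a reader might infer. One is that objective 3 as a whole cannot be answered. It can be for lacerations at patient level, and it may be for hematomas once the text is coded. The other is that uncorrected hematoma effects would be wrongly assigned to skin tone. That would require hematoma location to be associated with skin tone among the patients analysed, and the documents give no reason to expect it.

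What the objection does not remove is that swelling has no field and that the location text has no coding rule. The same form already structures comparable information: CT bleeds have eight area-by-side dropdowns and skull fracture location is multi-select. Side or area not noted at the bedside may not be recoverable later from unstructured text.

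**Conclusion.** The concern holds in a limited form. On swelling it is definite: the objective names it and the listed data cannot address it. On hematoma it is conditional: used alone, the merged flag understates the effect of blood under a probe by the face-only share f. That share is unknown, and the percentages and power values above are illustrations. The result also assumes that a face-only hematoma leaves the reading unchanged.

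The consequence is confined to exploratory objective 3 and to the scalp hematoma term in the regression. The primary sensitivity and specificity estimates do not use these fields. The change is still worth making during accrual, because it is cheap then and may not be possible afterwards.

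**What to change.** 1. Add a yes/no swelling item to Appendix A, ideally by scanned area and side, or delete swelling from objective 3.
2. Add a structured location item for extracranial hematoma by area and side, using the device's own probe positions. Count the forehead as a probe site, and record hematoma elsewhere on the face separately.
3. For patients already enrolled, code `scalp_text` to a single indicator of hematoma at a probe site. The coder should not see the `infra_1` or CT results. Entries too vague to place should be reported as such.
4. State in Section 15 that this indicator, not the merged flag, is the exposure in the regression and in objective 3, and that lacerations are analysed at patient level through `scalp_injury`.

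The cost is a few extra tick boxes at an examination that already takes place, and some recoding time. Sample size and the primary analysis do not change.
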